# Assay to be carried out until evidence of T cell recovery

\*\*\* Pre-gene therapy assay should be carried out only if not already done at diagnosis

\*\*\*\* Sample are stored but analysed retrospectively only in case sample at 1 year visit or 3 year visit are positive

**PHA** - phytohaemagglutinin stimulation, **Ig** – immunoglobulin, **TCR** - T cell receptor, **RCL** - replication competent lentivirus, **TREC** - TCR excision circles, **PCR** - polymerase chain reaction, **SCLN** - save cells in liquid nitrogen

## 4 Study Objectives

### 4.1 Primary Objectives

The primary objective is to assess the safety and efficacy of EFS-ADA LV mediated gene therapy, the Investigational Medicinal Product (IMP) for treatment of ADA-SCID patients. This will be achieved via the following specific objectives:

#### Efficacy

- To assess overall survival and event-free survival at 1 year for subjects treated with IMP and compare with patients treated with allogeneic HSCT
- To assess at each visit engraftment success and resulting immunological and metabolic effects in IMP treated subjects using:
  - Vector copy numbers in peripheral blood leukocytes
  - Cellular and humoral immune system recovery
  - ADA enzyme activity and reduction in dATP in peripheral blood cells

#### Safety

- To assess clinical, haematological and immunological progress of subjects
- To assess vector integration sites and clonal proliferation. This analysis will be performed at a specialised laboratory in Germany and the data will be reviewed and interpreted by the Principal Investigator (PI) and the study team

### 4.2 Secondary Objectives

The secondary objectives are to:

- Compare overall survival and event-free survival at 2 and 3 years between patients treated with IMP and patients treated with allogeneic HSCT
- Determine the percentage of IMP treated patients requiring immunoglobulin replacement therapy at all evaluation points from 18 months onwards
- Compare frequency of infections, and growth of pathogenic microorganisms over 3 years
- Evaluate the longitudinal clinical effect in terms of improved immunity
- Evaluate tolerability of conditioning regimen. These data will be reviewed and interpreted by the PI and the study team
- Evaluate feasibility of the transduction procedure. These data will be reviewed and interpreted by the PI and the study team.

## 5 Endpoints

### 5.1 Primary Endpoints

Primary endpoints for this study are:

- Overall survival at 1 year for patients treated with IMP.
- Event-free survival at 1 year for patients treated with IMP.

- Vector copy number in the cells at each study visit.
- Changes in T cell number, function and circulating immunoglobulin levels at each study visit.
- dATP and ADA enzyme activity in erythrocytes at each study visit.

The following endpoints will be analysed at a specialist laboratory in Germany and the results will be reviewed and interpreted by the PI and the study team, so these will not be included in this Statistical Analysis Plan (SAP).

- Frequency of vector integration into known proto oncogenes.
- Frequency of clonal expansion associated with vector integration near proto oncogene.

## 5.2 Secondary Endpoints

- Overall survival and event-free survival at 2 years and 3 years
- Frequency of infections (evaluated at 1, 2 and 3 years after treatment)
- TRECS after 2 years post-gene therapy
- Requirement for immunoglobulin replacement therapy (IgRT) and serum immunoglobulin levels for IgA, IgG and IgM.
- Feasibility of the transduction procedure assessed by availability of greater than  $0.5 \times 10^6$  CD34+ cells/kg after transduction; undetectable RCL (determined retrospectively); and CD45+ cell viability after transduction equal to or greater than 50%, in accordance with the final product release criteria. These data will be reviewed and interpreted by the PI and the study team and so will not be included in this SAP.

## 5.3 Additional Endpoints

Additional endpoints for this study are:

- T cell V $\beta$  panel
- Phytohaemagglutinin (PHA) stimulation result
- CD3 stimulation
- Vector integration analysis result
- Bone marrow aspirate (if performed)
  - Morphology (Normal/ Abnormal).
  - Integration (Normal/ Abnormal).
  - Vector copy number in BM-MNC.
- Tetanus vaccination response

## 6 Timing of Analyses

The statistical analyses of data from this study will be performed in four stages:

Interim look:

- Performed after all on-study subjects have completed 6 months of follow-up post infusion
- Descriptive statistics for all available data

- Comparisons between IMP treated subjects and HSCT control cohorts of demographics and overall survival

Primary analysis:

- Performed after all on-study subjects have completed 12 months of follow-up post infusion
- Descriptive statistics for all available data
- Comparison to HSCT control cohorts on overall and event-free survival at 12 months (primary efficacy endpoints), use of immunoglobulin replacement therapy (IgRT) and infection rate (key secondary endpoints).

Long-term follow-up analysis:

- Performed after all on-study subjects have completed 2 years of follow-up post infusion
- Descriptive statistics for all available data
- Comparison to HSCT control cohorts on overall and event-free survival at 2 years, use of immunoglobulin replacement therapy (IgRT) and infection rate (key secondary endpoints).

End of study analysis:

- Performed after all on-study subjects have completed the study (3 years of follow-up post infusion)
- Descriptive statistics for the complete study cohort
- Comparison to HSCT control cohorts on overall and event-free survival at 3 years, use of immunoglobulin replacement therapy (IgRT) and infection rate (key secondary endpoints).

## 7 Analysis Populations

### 7.1 Efficacy Population

#### IMP Treated Subjects

The study protocol recruited 10 subjects with a diagnosis of ADA-SCID to be treated with IMP at GOSH. These subjects will be known as the “on-study” subjects.

In addition, a group of subjects were treated under a Compassionate Use Programme (CUP under GOSH Special License) either because the study was not yet open and urgent treatment was needed, because they were outside of the inclusion/exclusion criteria or because they followed a different process (i.e., received the IMP in two infusions). These subjects followed the same study schedule as the on-study subjects.

The primary efficacy population for analysis will consist of the on-study IMP treated subjects. A secondary efficacy population will consist of all IMP treated subjects (on-study and CUP)

### HSCT Control Patients

The primary efficacy population from the HSCT historical control cohort will consist of ADA-SCID patients without a medically eligible HLA-matched sibling/family donor and treated with HSCT at Great Ormond Street Hospital (GOSH) from the year 2000 onwards.

Secondary efficacy populations will comprise:

- ADA-SCID patients with matched related donors treated with HSCT at GOSH from the year 2000 onwards;
- the complete HSCT historical control cohort consisting of ADA-SCID patients with any type of donor treated with HSCT at GOSH from the year 2000 onwards.

## **7.2 Safety Population**

The safety population will consist of all IMP treated subjects (on-study and CUP) and the complete HSCT historical control cohort consisting of ADA-SCID patients with any type of donor treated with HSCT at GOSH from the year 2000 onwards.

## **8 Statistical Methods**

In general, continuous variables will be summarised using the mean, standard deviation, median, minimum, maximum and number of subjects. Categorical variables will be summarised using number of subjects and percentages.

For all summaries, the IMP treated subjects will be summarised in the groups of on-study only and on-study plus CUP subjects. The HSCT controls will be summarised in the groups of those without a matched related donor, those with a matched related donor and all subjects.

### **8.1 Subject Disposition**

#### **8.1.1 Summary of Populations**

Number (%) of subjects enrolled (signed informed consent), treated, and in efficacy and safety populations will be summarised for the IMP treated and HSCT control groups. The denominator for the percentages will be the number of subjects enrolled.

Should any subjects be excluded from any of the analysis populations, a listing will be produced for these subjects noting the reason for exclusion.

#### **8.1.2 Summary of Withdrawals**

Number (%) of subjects who completed the study period will be summarised along with the reason for study withdrawal. The denominator for the percentages will be the number of subjects treated.

At the interim look, the primary analysis and the long-term follow-up analysis, the number (%) completing the designated follow-up period, and ongoing in the study will also be summarized.

Should any subjects have withdrawn from the study, a listing will be produced for these subjects noting the reason for study withdrawal, and the time since infusion at withdrawal.

## **8.2 Demography and Baseline Characteristics**

Demography and baseline characteristics will be summarised for the safety population.

### **8.2.1 Demography**

Age in months for the IMP treated on-study subjects will be calculated as:

$$12 * (\text{date informed consent signed} - \text{date of birth}) / 365.25.$$

Age in months for the IMP treated CUP subjects and the HSCT controls will be captured on the eCRF.

Age in months will be summarized for the IMP treated and HSCT control groups. Sex, ethnicity, location, weight and height at screening will be summarised for the IMP treated on-study group.

### **8.2.2 ADA Deficiency Diagnosis**

Age at diagnosis in months will be calculated for the IMP treated subjects (on-study and CUP) as:

$$12 * (\text{date of diagnosis} - \text{date of birth}) / 365.25.$$

For the HSCT control groups, the age at diagnosis will be recorded on the eCRF.

Time since diagnosis in months will be calculated as:

$$12 * (\text{date of transplant} - \text{date of diagnosis}) / 365.25,$$

or, for HSCT control subjects for whom the dates were not recorded, as:

$$\text{age in months at transplant} - \text{age in months at diagnosis}.$$

Age at diagnosis and time since diagnosis will be summarized using descriptive statistics for the IMP treated subjects and HSCT control groups. In addition, the number (%) of subjects with each method of diagnosis (DNA sequencing/ confirmed absence of <3% enzymatic activity/ unknown) will be summarized. For DNA sequencing, the details of mutations, exons and polymorphisms will be listed.

### **8.2.3 Disease Treatment History**

Number (%) of IMP treated subjects who previously received PEG-ADA treatment, receiving immunoglobulin replacement therapy, receiving infection prophylaxis, any previous BM or PBSC transplant (with the outcome) will be summarized.

## **8.2.4 Medical History**

The number (%) of subjects reporting medical history in each category will be summarised for the IMP treated and the HSCT control groups.

## **8.2.5 Infection at Screening**

The number (%) of IMP treated subjects reporting active infections at screening will be summarised overall and by localisation/event type.

## **8.2.6 Coagulation Tests**

Coagulation tests (partial thromboplastin time, APT, thrombin time and fibrinogen) will be evaluated at screening for the IMP treated subjects and summarised using descriptive statistics.

## **8.2.7 Glomerular Filtration Rate (GFR) at screening**

Distribution volume, half-life, glomerular filtration rate and corrected glomerular filtration rate will be summarised for the IMP treated subjects using descriptive statistics. In addition, the number (%) of subjects with a distribution volume outside the normal range that was considered to be clinically non-significant or clinically significant will be summarized.

## **8.2.8 Virology Tests**

The number (%) of IMP treated subjects with positive results for CMV, EBV, Adenovirus, HIV1, HIV2, VZV, Hep A, Hep B, HSV, Hep C, Syphilis, HTLV1, HTLV2, Toxoplasma will be summarised.

## **8.2.9 Cardiopulmonary Tests at Screening**

A chest x-ray, ECG, Echocardiogram and lung function test will be carried out at screening. The results of each test will be categorized as normal/ abnormal, not clinically significant/ abnormal, clinically significant. The number (%) of IMP treated subjects with evaluations falling into each category will be summarised for each test. Should any subject have an abnormal evaluation with the clinical significance assessment missing, this will be categorized as “abnormal unknown clinical significance” and this category will be added to the summary.

In addition, details of any clinically significant findings will be listed.

## **8.2.10 General Tests at Screening**

Dental, audiology and maternal engraftment studies tests will be carried out at screening. The results of each test will be categorized as normal/ abnormal, not clinically significant/ abnormal, clinically significant. The number (%) of IMP treated subjects with evaluations falling into each category will be summarised for each test. Should any subject have an abnormal evaluation with the clinical significance assessment missing, this will be categorized as “abnormal unknown clinical significance” and this category will be added to the summary.

In addition, details of any clinically significant findings will be listed.

### **8.2.11 Harvest for Gene Therapy**

The number (%) of IMP treated subjects with each blood type and with stem cells from each source (leukapheresis/bone marrow) will be summarised.

For subjects with a leukapheresis harvest, the dose of G-CSF administered on Days 1-6, the details of any plerixafor administration and the CD34+ cell counts in blood will be listed.

For subjects with a leukapheresis harvest on multiple days, the total number of cells will be the sum across the days. The number of cells stored for the gene therapy will be calculated as the total cell count – number of back up cells. Body weight at harvest, total number of nucleated cells, total CD34+ cell count and CD34+ cell count excluding back-up cells will be summarised using descriptive statistics.

### **8.2.12 Back-up Harvest**

The number (%) of IMP treated subjects for whom  $\geq 3 \times 10^6$  CD34+ cells/kg have been stored as back-up will be summarised along with the CD34+ count. For those that have a back-up harvest, the number (%) with stem cells from each source (leukapheresis/bone marrow) will be summarized using the number with a back-up harvest as denominator for the percentage. For those without a back-up harvest, the number (%) with each reason for not performing the harvest will be summarized using the number without a back-up harvest as denominator for the percentage.

### **8.2.13 Myeloablative Conditioning**

The number (%) of IMP treated subjects for whom conditioning was done will be summarised along with the body weight, height, BSA, busulfan dose and busulfan AUC.

### **8.2.14 IMP Administration**

Age at transplant in months will be calculated for the IMP treated subjects (on-study and CUP) as:

$$12 * (\text{date of transplant} - \text{date of birth}) / 365.25.$$

The duration of IMP infusion (in minutes) will be calculated as (end time – start time)/60.

The number (%) of subjects who received the IMP infusion and for whom the entire content of the bag was infused will be summarised along with the age at transplant, the duration of infusion, CD34+ cell dose, cell viability and volume.

### **8.2.15 Transplant Details for the HSCT Controls**

For the HSCT control groups, the age in months at transplant will be recorded on the eCRF.

Age (months) at transplant, number of CD34+ cells/kg transplanted and busulfan dose, if appropriate, will be summarized for each HSCT control group using descriptive statistics.

Number (%) of subjects with each type of transplant cells, transplant donor type, conditioning type, receiving enzyme replacement therapy (ERT) prior to the transplant, receiving ERT after the transplant, receiving IgRT prior to the transplant, receiving IgRT after the transplant and receiving gene therapy after the transplant will be summarized for each HSCT control group.

## 8.2.16 Exposure

Duration of follow-up in months will be calculated for the IMP treated subjects as:

$$12 * (\text{date of final evaluation} - \text{date of infusion} + 1) / 365.25.$$

For the HSCT controls, the duration of follow-up will be recorded on the eCRF.

Duration of follow-up will be summarized for the IMP treated and the HSCT control groups using descriptive statistics. In addition, the total subject-years of follow-up in each treatment group will be presented.

## 8.3 Efficacy Analyses

The primary comparison for all efficacy analyses will be between the IMP treated on-study subjects and the allogeneic HSCT controls treated at GOSH without a matched related donor. Secondary comparisons will be between:

- the IMP treated on-study subjects and the HSCT controls treated at GOSH with a matched related donor;
- the IMP treated on-study subjects and the total group of HSCT controls;
- all IMP treated subjects (on-study and CUP) and the HSCT controls treated at GOSH without a matched related donor;
- all IMP treated subjects (on-study and CUP) and the HSCT controls treated at GOSH with a matched related donor;
- all IMP treated subjects (on-study and CUP) and the total group of HSCT controls.

### 8.3.1 Primary Efficacy Endpoints

#### 8.3.1.1 Overall Survival at 12 Months

Overall survival will be evaluated using the time in months from transplant to either the subject's death or their last evaluation calculated as:

$$12 * (\text{date of death/last evaluation} - \text{date of transplant}) / 365.25,$$

or, for HSCT control subjects for whom the dates were not recorded, as:

$$\text{age in months at death/end of follow-up} - \text{age in months at transplant}.$$

The number (%) of subjects who were still alive at 12 months post-transplant will be summarised. For the purpose of this analysis, any subject who withdrew from the study prior

to 12 months, who was known to be alive at the last evaluation, will have a status of “unknown”. The proportion and exact 95% confidence interval (CI) for survivors at 12 months post-transplant will be calculated for each of the IMP treated and HSCT control groups along with the difference in proportions (with 95% CI) between the IMP treated and control groups, excluding those with unknown status.

Overall survival in each treatment group will also be represented using a Kaplan-Meier curve for time to death. For the purpose of this analysis, any subject who withdrew from the study prior to 12 months and was known to be alive at the last evaluation will be censored at the date of their last evaluation. If appropriate, the proportion alive at 12 months and the associated 95% CI will be estimated for each treatment group from the Kaplan-Meier curve along with the median survival time (and interquartile range), if they can be estimated from the data.

If there is at least one event in each group, the log-rank test will be used to compare the difference in survival curves between the IMP treated and HSCT control groups.

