### 4.1 Patients treated with gene therapy (on study)

- Patients will be selected on the basis of inclusion and exclusion criteria as detailed below
- A back-up harvest will be retained in case of failure of reconstitution following conditioning and re-infusion of transduced cells
- For the transduction protocol (see appendix 3 for schematics), CD34+ cells will be purified from G-CSF mobilised Peripheral Blood Stem Cell (PBSCs) recovered by leukapheresis (Plerixafor may be added to enhance mobilization), whenever possible or from bone marrow harvested under general anaesthetic. Back-up cells of  $3 \times 10^6$  CD34+ cells/kg will be stored from a single procedure if sufficient cell counts available (and if not previously stored). The remaining CD34+ cells will be taken forward for transduction. If  $< 3 \times 10^6$  CD34+ cells/kg are harvested from the back-up, the patient will be withdrawn from the study

- Patients in whom of  $<1 \times 10^6$  CD34+ cells/kg are available for transduction will not proceed to conditioning, will be withdrawn from the study and will be offered a repeat harvest in approximately. 3 months
- Patient conditioning will be initiated immediately after bone marrow or PBSC collection (busulfan iv. weight adjusted dose)
- After purification, CD34+ cells will be immediately transduced with the lentiviral vector as detailed below, then evaluated for sterility, cell count, and viability, and immediately infused into patients
- Several other tests for safety including testing for RCLs will be performed on re-infused cells and results will be recorded retrospectively
- If less than  $0.5 \times 10^6$  viable transduced CD34+ cells/kg are returned to the patient, then back-up bone marrow/PBSCs will be returned and patients will be withdrawn from the study
- PEG-ADA will be withdrawn one month (+/- 6 days) post-infusion
- If there is no bone marrow recovery by 6 weeks (ANC $<0.5 \times 10^9/L$  or platelets  $< 20 \times 10^9/L$ ) the back-up harvest will be re-infused
- Patients will be followed up on study at 1 month, 6 weeks, 3, 6, 9, 12, 18, 24, 30 and 36 months post gene therapy. Visit windows will be +/- 5 days for visits at 1 month, 6 weeks and +/- 2 weeks for visits at 3, 6, 9, 12, 18, 24, 30 and 36 months post gene therapy If after 180 days there is no evidence of the transgene in PBMCs by qPCR or there is no evidence of T cell recovery, then patients will re-start PEG-ADA and will be withdrawn from the study

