PEG-ADA may be restarted at PIs discretion prior to this time point on clinical grounds e.g infective problems or delayed immune reconstitution and at this stage will be withdrawn from the study.

[figure not shown]

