### **8.4 Withdrawal of individual subjects**

A patient can withdraw or be withdrawn from protocol treatment in the study at any time from enrolment until the transduced CD34+ cells have been administered. Once a patient has been administered the transduced CD34+ cells study treatment is complete.

- Patients from whom  $<3 \times 10^6$  CD34+ cells/kg are harvested for the back-up, will be withdrawn from the study prior to conditioning and offered a repeat harvest
- Patients from whom  $<1 \times 10^6$  CD34+ cells/kg are harvested for transduction, will be withdrawn from the study prior to conditioning and offered a repeat harvest
- If less than  $0.5 \times 10^6$  viable transduced CD34 + cells/kg are returned to the patient, then back-up bone marrow/PBSCs will be returned and patients will be withdrawn from the study
- If after 180 days there is no evidence of the transgene in PBMCs by qPCR or there is no evidence of T cell recovery, then patients will re-start PEG-ADA and will be withdrawn from the study

PEG-ADA may be restarted at PIs discretion prior to this time point on clinical grounds e.g infective problems or delayed immune reconstitution and at this stage will be withdrawn from the study. The decision for patients to remain off PEG-ADA is dependent on a combination of factors including:

- 1) metabolic detoxification as assessed by sustained red blood cell dATP levels  $<250$  umol/l
- 2) T cell recovery as assessed by absolute T cell numbers (CD3+ cells)  $>300$  cells/mm^3
- 3) engraftment of gene modified cells as assessed by vector copy number in CD3+ cells  $>0.05$  ( $>5\%$  of total T cells)

Subjects who wish to discontinue from the study at any time are free to do so. However the reasons for discontinuation should be documented by the investigator if possible.

Patients who withdraw from the study after administration of the transduced CD34+ cells for reasons other than those given above will be encouraged to have follow-up investigations so that the consequences of the administration can be documented and analysed.

Any patient withdrawn prior to administration of transduced CD34+ cells will be replaced in the study.

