### **8.3.1.2 Event-free Survival at 12 Months**

Event-free survival will be evaluated using the time in months from transplant to either the first event or their last evaluation calculated as:

$$12 * (\text{date of event/last evaluation} - \text{date of transplant}) / 365.25,$$

or, for HSCT control subjects for whom the dates were not recorded, as:

$$\text{age in months at death/end of follow-up} - \text{age in months at transplant}.$$

For the purpose of this analysis, the events of interest are:

- death;
- reinstitution of PEG-ADA ERT;
- requirement for a second transplant.

Event-free survival will be summarized in the same way as overall survival described in Section 8.3.1.1.

In addition, if there are any events (other than death), the time to each event will be summarized in a similar manner to the overall event-free survival.

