## **8.3.2 Secondary Efficacy Endpoints**

### **8.3.2.1 Overall and Event-free Survival at 2 and 3 Years**

Overall and event-free survival at 2 and 3 years will be summarized in the same way as for the analyses at 12 months described in Sections 8.3.1.1 and 8.3.1.2.

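### The 12-month survival proportion drops subjects for leaving the study, not for missing vital status, and on one reading of the protocol treatment failure makes gene therapy patients leave

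*SAP*

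**What the plan says.** **Overall survival (OS).** Under SAP 8.3.1.1, a subject who withdrew from the study before 12 months "who was known to be alive at the last evaluation, will have a status of" unknown. The group comparison is the "difference in proportions (with 95% CI) between the IMP treated and control groups, excluding those with unknown status". The Kaplan-Meier analysis in the same section keeps these subjects but censors them at their last evaluation. SAP 8.3.2.1 extends the approach: "Overall and event-free survival at 2 and 3 years will be summarized in the same way as for the analyses at 12 months".

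**Event-free survival (EFS).** SAP 8.3.1.2 lists death, reinstitution of PEG-ADA and need for a second transplant as events. It states: "Event-free survival will be evaluated using the time in months from transplant to either the first event or their last evaluation". It then adds: "Event-free survival will be summarized in the same way as overall survival described in Section 8.3.1.1".

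**Withdrawal after infusion.** Protocol 8.4 says that if there is no transgene or no T cell recovery after 180 days, "then patients will re-start PEG-ADA and will be withdrawn from the study". For an earlier PEG-ADA restart on clinical grounds, Protocol 4.1 gives as examples infection or "delayed immune reconstitution and at this stage will be withdrawn from the study". For a low returned cell dose, Protocol 4.1 says "then back-up bone marrow/PBSCs will be returned and patients will be withdrawn from the study".

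**Text pointing the other way.** Protocol 5.4 and 7.5.8 describe a PEG-ADA restart at the investigator's discretion without mentioning study withdrawal, and 7.5.8 allows restarted PEG-ADA to be stopped again. The off-study criteria in Protocol 8.5 cover withdrawal before infusion, withdrawn consent and loss to follow-up. Protocol 8.6 ends data recording only for withdrawal before infusion and for withdrawn consent. Neither section names an infused patient whose treatment failed.

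**The concern.** A subject should be unknown at 12 months because nobody can establish whether the child is alive. The SAP attaches the label to an administrative act instead. If Protocol 4.1 and 8.4 govern, that act follows from failed engraftment, failed immune recovery or a return to enzyme replacement, so the exclusion is related to outcome.

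It is also one-sided by rule. The HSCT controls are retrospective routine-care data (Protocol Appendix 8, section 4), and no withdrawal-for-failure rule applies to them. The documents give neither the number of controls nor their loss to follow-up, so the net imbalance cannot be quantified.

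The primary efficacy population is 10 on-study subjects (SAP 7.1), so each one dropped removes a tenth of the group. Follow-up may also be thinner for these patients. Protocol 8.4 encourages follow-up investigations after infusion for those who withdraw for reasons other than the ones it lists, which leaves out the failure withdrawals.

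**Working it through.** The documents give no sample-size or precision target for OS, so there is no planned figure to reproduce.

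**Inputs**
- On-study subjects: 10 (SAP 7.1).
- Earliest scheduled failure decision: 180 days, which on the SAP's month scale is 12 × 180 / 365.25 = 5.9 months. This is inside the 12-month window.
- Number withdrawn for failure before month 12: not in the documents. I assume 3 of 10 and show 1 to 5. Protocol Table 1 is only a rough guide: 3 + 4 + 3 + 1 = 11 of 36 (30.6%) were not off enzyme, in earlier gammaretroviral trials with mixed follow-up.
- Intervals: exact (Clopper-Pearson) 95%. When all n survive, the lower limit is 0.025^(1/n). For n = 7 this is 59.0%, and for n = 10 it is 69.2%.

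**Crude 12-month OS, 3 withdrawn**

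| Situation | SAP rule | Known status used |
|---|---|---|
| No deaths | 7/7 = 100% (59.0–100) | 10/10 = 100% (69.2–100) |
| One retained patient dies, the three withdrawn live | 6/7 = 85.7% (42.1–99.6) | 9/10 = 90% (55.5–99.7) |
| One withdrawn patient dies; death counted, two survivors unknown | 7/8 = 87.5% (47.3–99.7) | 9/10 = 90% (55.5–99.7) |
| One withdrawn patient dies; death not counted | 7/7 = 100% (59.0–100) | 9/10 = 90% (55.5–99.7) |

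For a given control proportion, the shift in the group difference equals the shift in the IMP proportion: 85.7 − 90 = −4.3 points, 87.5 − 90 = −2.5 points, or 100 − 90 = +10 points.

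**Range for the assumption**
- No deaths: 1 withdrawn gives 9/9 (66.4–100) and 5 withdrawn gives 5/5 (47.8–100), both against 10/10.
- One retained death: 1 withdrawn gives 8/9 = 88.9% (51.8–99.7) and 5 withdrawn gives 4/5 = 80% (28.4–99.5), both against 9/10.

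**Kaplan-Meier.** Take 10 subjects, three of them censored at 5.9 months, and one retained death.
- Death at month 3: S(12) = 1 − 1/10 = 90.0%.
- Death at month 9: S(12) = 1 − 1/7 = 85.7%, the same as the crude 6/7.

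Censoring therefore helps only when the death comes before the withdrawals. If the three are followed to month 12, both timings give 90.0%.

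**EFS.** Three PEG-ADA restarts and no other event give 7/10 = 70% (34.8–93.3) under the first-event definition. Applying the unknown rule literally would give 7/7. The listed event makes 7/10 the natural result, but the SAP does not say that an event overrides the unknown label. A restart made because of withdrawal (Protocol 5.4) can also be dated after the withdrawal.

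**The case against.** The strongest reply is that infused failures may not leave the study at all. If Protocol 8.5 governs, an infused patient goes off study only by withdrawn consent or loss to follow-up, and the SAP's unknown class is then nearly what it should be. Protocol 8.4 itself opens by limiting withdrawal from protocol treatment to the time before infusion. This reading is tenable, and it means the root problem is partly a protocol inconsistency. It does not clear the SAP, whose wording keys on withdrawal while two protocol sections order it.

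A reader might infer that the rule inflates gene therapy survival. The documents do not support that as the expected result. OS time runs to death, deaths are reported whatever their cause (Protocol 11.4.1), and they are listed (SAP 8.4.1.3). If known deaths count, dropping only survivors can lower the proportion or leave it at 100%, but cannot raise it. Inflation needs a death after withdrawal to go uncounted. That remains possible, because such a patient was also alive at the last evaluation and the SAP does not say which rule prevails.

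A reader might also bound the result at 7/10 by supposing that all three withdrawn patients die. That is an arithmetic limit only. Protocol Table 1 reports 100% survival, and Protocol 5.1.3 says that earlier failures went back to PEG-ADA without harm, although with another vector. Nor should the low-dose route carry weight for on-study subjects. Protocol 10.4 makes that cell dose the release threshold, and Appendix 9 gives unmet release specification as a reason for compassionate use instead.

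The plan does offer some protection. Withdrawals are listed with reason and time since infusion (SAP 8.1.2), and the comparisons are descriptive (Protocol 8.9.2). This makes the loss visible but does not correct it. The sensitivity analyses in SAP 8.3.4 are triggered by major protocol violations, and a withdrawal that the protocol orders is not one.

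**Conclusion.** The point stands in a limited form. As written, the SAP discards known 12-month outcomes from a primary endpoint in a 10-patient group. On the reading set by Protocol 4.1 and 8.4, it does so because treatment failed, in the gene therapy group only. The protocol contradicts itself on whether that reading applies, and the passages must be reconciled.

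With 3 of 10 withdrawn, the likely cost is a lower confidence limit of 59.0% where 69.2% was available, or an estimate about 4 points too low if one retained patient dies. The only upward error, 10 points for one death, depends on a death after withdrawal going uncounted. These sizes rest on the assumed number withdrawn and on vital status being obtainable. The direction of bias is not fixed. For EFS the issue is a drafting gap, and the documents do not support an expectation that PEG-ADA restarts will be dropped.

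**What to change.** - In SAP 8.3.1.1 and 8.3.2.1, classify every infused subject by known vital status at 12, 24 and 36 months, regardless of study withdrawal, and count deaths after withdrawal.
- In the Kaplan-Meier analysis, censor at the date last known alive.
- Keep the unknown category for subjects whose vital status at the time point cannot be obtained (withdrawn consent or true loss to follow-up), and report how many there are in each group.
- In SAP 8.3.1.2, state that a known event by the time point always counts, whether it falls before, at or after study withdrawal.
- Reconcile Protocol 4.1 and 8.4 with 5.4, 7.5.8, 8.5 and 8.6 on whether infused patients whose treatment failed remain in study data collection. This concerns data capture only and implies no change to clinical management.

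The cost is a few sentences in the SAP, a protocol wording correction and a little vital-status retrieval. The lifelong follow-up in Protocol 11.4.4 should help, but that section is about safety reporting and not outcome capture in the eCRF. Referrals are also worldwide (Protocol 5.1), so some status may stay missing. Reported OS or EFS could be slightly less favourable where a later death or event is now counted.
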